Total No. of items/duration of assassment	0, 21-23, 24a-1, 23, 20a-d	136 to 166/**
rotar no. or items/duration or assessment		24 to 38
		min***

depending on whether respondent skips out of sections *estimate based on pilot testing

- 878 For the prospective donor cohort HRQOL studies at 1 year and 2 years post-donation, the
- assessments are identical to those at 3 months and 6 months in the prospective cohort, except that the
- 880 10-item Posttraumatic Growth Inventory is included. This will increase the estimate time to 26 to 40
- 881 minutes.

882 **4.3.9** Sample size and power calculations

883 We anticipate a total sample size of 375 liver donors. This sample size estimate is based on the numbers of living liver donor transplants performed at A2ALL-2 sites during the past 3 years and the 884 885 expectation that we would enroll subjects for a total of two years going forward (allowing for follow-up of the last subjects enrolled before the end of A2ALL-2 funding). It also assumes 20% to 886 887 30% of prospective donors will refuse to enroll. Finally, across the study period, we assume that 888 attrition will range between 10% to 15% (based on our past experience with donor and other 889 transplant-related samples using the type of survey strategies proposed). Thus, by the final 890 assessment wave, we expect to have a sample of 319 to 337 liver donors.

- 691 Given expected refusals to enroll and expected attrition, even with 319 liver donors (the worst-case
- scenario) we would have power exceeding .995 to detect small differences of less than 4% between a
- 893 "case" rate of problems in a given HRQOL domain (e.g., rate of clinically significant psychiatric
- symptomatology) and a population/normative rate (Primary Aim 2, Objectives b.1. and b.2.). For
- 895 Objective b.3., we would utilize the same strategies as those described for the long-term follow-up 896 cohort. With a sample of 319, utilizing a regression approach to examine donor outcome status at a
- given time point (see also Section 4.3.10 below), with two-tailed alpha at .05, as many as 8
- 898 covariates controlled, and allowing the covariates themselves to have moderate-sized associations
- 899 with the outcome, then our power to detect even conventionally small⁶⁸ differences in proportions or
- 900 means will exceed .80. We note that we will not restrict our analyses to consideration of outcomes

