Protocol. Donor and recipient height, weight, and BMI will be recorded to normalize graft size and
the extent of resection. Special attention will be paid to recipient parameters associated with the
presence of portal hypertension including ascites and varices. Baseline recipient cross-sectional
imaging will define liver and spleen volumes.

- 933 Standard surgical techniques will be used for the donor and recipient operations. Right lobe, left
- lobe, or left lateral segment donation and transplantation will be performed based on clinical
- 935 parameters for graft selection.
- 936 The following will be recorded for donors: duration of surgery, hemodynamics, blood, and fluid 937 replacement. Liver biopsy will be obtained at baseline and after parenchymal transection before
- 938 devascularization of the graft. The liver graft will be weighed upon extraction. Donor pressure and
- flow measurements were collected as part of the A2ALL Core protocol, V1.9. We sought to define
- 940 the values and variability of these observations in healthy livers. The value of these data was 941 weighed against the intrusiveness of the probe insertion and portal vein puncture. From the outset we
- 941 weighed against the intrusiveness of the probe insertion and portal vein puncture. From the outset we 942 planned interim analyses with the expectation that we would stop collecting donor data after an
- 943 adequate sample of reliable data was collected. The Surgical Innovations Committee met in Nov.
- 944 2011 and determined that the amount and quality of data was inadequate and donor collection should
- continue. A follow-up review was conducted on April 16, 2012 with data on 90 subjects. Key values
- 946 were reviewed and deemed satisfactory for the purposes of the study and the Committee 947 recommended that further data collection be suspended in the interest of donor safety. This was
- 947 recommended that further data collection be suspended in the interest of donor safety. This was 948 supported unanimously by the Steering Committee the following day and collection has been
- 949 suspended.

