We anticipate enrollment to average 10 recipients annually per site with a potential enrollment of 180 recipients over a 2-year period. This sample size estimate is based on the numbers of living liver donor transplants performed at A2ALL-2 sites during the past 3 years and the expectation that we would enroll subjects for a total of two years going forward (allowing for follow-up of the last subjects enrolled before the end of A2ALL-2 funding). It also assumes 20% to 30% of prospective recipients will refuse to enroll. Statistical analysis

- 1001 The chief aim of the analyses is to provide descriptive information about relation between hepatic
- 1002 hemodynamics and graft size and functional outcomes. Standard approaches to examine
- 1003 distributions (e.g., descriptive statistics, box plots, histograms). We will attempt to identify
- 1004 correlations using regression analysis. Categorical comparisons between graft types will be
- 1005 examined to detect the effect of left lobe grafting.

10064.5Primary Aim 5: To compare the long-term histological outcomes in recipients of LDLT1007and DDLT with recurrent HCV infection

1008 **4.5.1 Study methods**

- 1009 The primary focus of this aim is to compare long-term outcomes (cirrhosis) of HCV recurrence in
- 1010 recipients of DDLT vs. LDLT. All participants from the Cohort A2ALL-1 study, including those
- 1011 whose donor was evaluated during the Retrospective era, will be eligible for inclusion. LDLT and
- 1012 DDLT recipients from the new A2ALL sites will be eligible if they had at least one potential donor
- 1013 present to the transplant center for evaluation, as per the original A2ALL-1 inclusion criteria. For
- 1014 these patients identified by the new sites, a waiver of consent for data extraction will be sought from
- 1015 their respective IRBs. for chart review if the patient is deceased or no longer followed. Subjects who
- 1016 received a transplant during the GAP era and meet the inclusion criteria will also be approached for
- 1017 consent or have their data collected under a Waiver of Consent as described above.
- 1018 With the goal of focusing on longer-term outcomes, surviving non-retransplanted recipients (LDLT
- and DDLT) will return to their transplant center at least 3 years post-LT for a comprehensive
- evaluation, including collection of blood for DNA (if not already collected as part of Aim 2) and

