1228 4.6.1.3 Participant Selection – Retrospective Component

- 1229 The lead investigator at each site will select up to three health care providers involved in post liver
- 1230 donation pain management: a liver transplant surgeon, an anesthesiologist, and the nurse transplant 1231 coordinator.
- 1232 4.6.1.4 Participant Selection – Prospective Component
- 1233 Inclusion Criteria

1234

- Adult living liver donors
- 1235 **Exclusion** Criteria
- 1236 History of chronic pain •
- History of narcotic use (routine scheduled narcotic use for treatment of a pain disorder 1237 1238 diagnosed and treated by a physician)
- 1239 Medically unstable at 48 hours post-donation surgery •
- 1240 Language barrier •
- 1241 4.6.1.5 Data elements
- 1242 **Retrospective Component:**
- 1243 Responses to retrospective survey (see Appendix E)
- **Prospective Component** 1244
- 1245 Demographic information as described in Section 4.1.3 •
- 1246 Intraoperative, perioperative and post-operative complication and hospitalization information • as described in Section 4.1.3 1247
- 1248 Responses to screening questions regarding history of chronic pain and narcotic use •
- Responses to the APS-POQ-R survey (see Appendix F) 1249 •
- 1250 4.6.1.6 Sample size and power calculations
- 1251 Retrospective Component: The unit of analysis is the clinical center, with a sample size of 9. This
- analysis will describe clinical practice at the 9 A2ALL centers and will not attempt to make 1252
- 1253 inference to a larger population.
- 1254 Prospective Component: We anticipate that approximately 200 future donors will be enrolled in 1255 A2ALL-2. Although it is unlikely that more than 200 donors will be accrued, enrollment will
- 1256 remain open during A2ALL-2 to allow as much power as possible to assess center effects and
- variables predictive of satisfaction with pain management. Because many of the study measures will 1257
- 1258 be presented descriptively, we first give the confidence interval (CI) width for, e.g., the true mean
- 1259 satisfaction score (0-10 scale) assuming a standard deviation of 2.0. With n=200, we will have 93%
- probability that the width of this CI will be no greater than +/-0.30. For comparing the satisfaction 1260 1261 scores at two of the 9 centers, say each with n=30 donors, we will have 90% power to detect a
- 1262 difference in means of 1.7. Sample size calculations were made using the SAS Power procedure
- 1263 (SAS Institute, Inc., Cary, NC).

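### Sections 4.3.9 and 4.4.4 forecast 375 donors and 180 recipients from the same stated basis; both cannot hold, and the prospective HRQOL power statements rest on the larger figure

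*Protocol*

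**What the plan says.** **Section 4.3.9 (Aim 3, prospective donor cohort).** "We anticipate a total sample size of 375 liver donors". The stated basis is the "numbers of living liver donor transplants performed at A2ALL-2 sites during the past 3 years". Recruitment is planned to last two years. Refusal is put at 20% to "30% of prospective donors will refuse to enroll", and this is already allowed for in the 375. Over the study the plan assumes that "attrition will range between 10% to 15" percent, which gives an expected 319 to 337 donors at the last wave. The section calls 319 the worst case. At that size it claims power above .995 for differences under 4 percentage points from a normative rate. It also claims power above .80 for conventionally small effects with up to 8 covariates. For mixed models it takes the whole enrolled cohort as the effective sample.

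**Section 4.4.4 (Aim 4, recipients).** "We anticipate enrollment to average 10 recipients annually per site with a potential enrollment of 180 recipients over a 2-year period". The volume source, the 3-year look-back, the two-year window and the 20% to 30% refusal match those in 4.3.9.

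**Section 4.6.1.6 (Aim 6, donor pain survey).** About 200 future donors are expected, and "it is unlikely that more than 200 donors will be accrued".

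**The concern.** A living donor transplant produces one donor and one recipient. Two forecasts that start from the same transplant count, cover the same enrolment period and apply the same refusal rate should give nearly the same total. Here one is about double the other, within one protocol and without comment.

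The power statements for the prospective part of a primary aim use only the larger total. If that total is too high, the stated worst case is not a worst case. Readers would then expect more precision on prevalence, and more ability to find risk factors for poor donor outcomes, than the cohort can give.

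**Working it through.** **Inputs.** 375 donors, 10% to 15% attrition, 319 to 337 at the last wave (4.3.9). 10 recipients per site per year, 2 years, 180 in total (4.4.4). 9 centers (4.6.1.6). About 200 donors (4.6.1.6).

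**1. Reproduce the plan's own figures.**
- Final wave = enrolled × (1 − attrition): 375 × 0.85 = 318.75 and 375 × 0.90 = 337.5. The stated 319 to 337 reproduces.
- Aim 4: 9 × 10 × 2 = 180. This reproduces.
- The 375 cannot be reproduced, because no transplant volume is given.

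**2. Compare the forecasts.**
- 375 / 180 = 2.08.
- 375 donors over 2 years at 9 sites is 375 / 18 = 20.8 per site per year, against 10 recipients.
- Before refusal of 20% to 30%, 375 enrolled implies 375 / 0.8 = 469 to 375 / 0.7 = 536 donors approached. The 180 implies 180 / 0.8 = 225 to 180 / 0.7 = 257 recipients approached. One transplant count cannot supply both ranges.

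**3. Final wave if the smaller forecasts hold.**
- From 180: 180 × 0.85 = 153 to 180 × 0.90 = 162.
- From 200: 200 × 0.85 = 170 to 200 × 0.90 = 180.

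**4. Illustrative power, two-sided alpha 0.05.** The protocol gives neither the normative rate nor the numerical meaning of a small effect, so the values below are assumptions.

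- *Two equal groups, d = 0.2, t-test.*
- *One-sample proportion against norm p0, with p1 = p0 + 0.04.* Power = Φ[(0.04 − 1.96·√(p0(1−p0)/n)) / √(p1(1−p1)/n)]. For n=319 and p0=0.10: (0.04 − 1.96 × 0.0168) / 0.0194 = 0.36, so power is 0.64.
- *Regression, one tested predictor plus 8 covariates, f² = 0.02, noncentral F.*

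| Test | n=319 | n=170 | n=153 |
|---|---|---|---|
| d = 0.2, equal groups | 0.43 | 0.25 | 0.23 |
| 4 points above a 1% norm | 0.99 | 0.93 | 0.92 |
| 4 points above a 5% norm | 0.84 | 0.63 | 0.59 |
| 4 points above a 10% norm | 0.64 | 0.42 | 0.39 |
| 4 points above a 30% norm | 0.35 | 0.21 | 0.20 |
| f² = 0.02, 8 covariates | 0.71 | 0.45 | 0.41 |
| same, covariates explain 13% of variance | 0.77 | 0.50 | 0.46 |

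The plan speaks of differences under 4 points, so the 4-point rows are the favourable end. At n=319, power above .995 appears only for a norm of about 0.5% or lower (0.997 at 0.5%, 0.991 at 1%).

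**The case against.** **The populations are not identical.** Aim 3 recruits English-speaking people approved for donation (4.3.6), some of whom may not reach surgery. Aim 4 takes recipients listed for a liver alone (4.4.2.1). This is true, but the English-language limit lowers the donor count, and nothing suggests that the other differences double it. The stated basis of both forecasts is transplants performed.

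**The documents do not say which forecast is right.** This stands. A reader might infer that the true number is 180 to 200, and that every prospective power figure therefore uses about twice the available sample. Without transplant volumes that is not established. Section 4.6.1.6 points the same way as 4.4.4, but only as secondary support. It speaks of future donors, possibly only those still to come when that aim was written. It gives no two-year window, and Aim 6 has its own exclusions (chronic pain, narcotic use, medical instability, language).

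**The count of 90 is not an accrual count.** Section 4.4.1 says "A follow-up review was conducted on April 16, 2012 with data on 90 subjects". A reader might turn this into a yearly enrolment rate. It counts donors with pressure and flow data, not donors enrolled, and Appendix D says that site initiation varied. It should not be used.

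**Much of the power shortfall has another cause.** This also stands. On the tests above, the claims are already missed at 319 for most assumed norms and for small effects. The accrual conflict makes this worse but does not create it.

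**The cohort is observational and takes all willing eligible donors.** The 375 is an expectation, not a stopping point, and description is a chief aim (4.3.10). That limits the severity, not the contradiction.

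**Conclusion.** The contradiction holds. Sections 4.3.9 and 4.4.4 state one basis and reach totals that differ 2.08-fold, and no stated eligibility difference plausibly accounts for it. The final wave of 319 to 337 and the 4.3.9 power statements therefore rest on a figure that the protocol itself contradicts.

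The size of the consequence is conditional. If 180 to 200 is right, the final wave is 153 to 180, about half of what is stated. The mixed-model argument would then start from 180 to 200 enrolled, which is below the stated worst case of 319. If 375 is right, the sample stands and it is the 180 in 4.4.4 that needs correcting.

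In either case, the claims of power above .80 for small effects and above .995 for differences under 4 points are not reproduced at n=319 under the assumptions shown, apart from the second claim at very low normative rates. This should be fixed. It does not threaten the design, because no eligibility rule, procedure, endpoint or analysis method depends on it.

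**What to change.** - Reconcile Sections 4.3.9, 4.4.4 and 4.6.1.6 to one donor-recipient accrual forecast. Show the site transplant volumes, the enrolment window and the refusal rate behind it, and say whether the Aim 6 figure counts all donors in the study or only those still to come.
- Unless the volumes justify 375, restate the expected final HRQOL sample as about 153 to 180.
- In either case, recompute the 4.3.9 power or detectable effects at the reconciled size. State the normative rate for each domain and the numerical effect size meant by small.

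The cost is protocol wording and one recalculation, and the resulting figures will be less favourable.

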- at only individual time points but will also utilize a mixed effects approach (which is appropriate
 both for interval and discrete outcomes). Power will be even greater under a mixed effect approach
- because such models allow for the inclusion of cases with incomplete data, and thus our effective
- sample size will be the total cohort enrolled. Therefore, even if we apply corrections for multiple
- 905 comparisons (given the fact that we will examine multiple domains of HRQOL), our power will
- 906 continue to exceed .80 for examining risk factor-outcome associations.

907 4.3.10 Statistical analysis

- 908 Similar to the long-term follow-up cohort, a chief aim of the analyses is to provide descriptive
- 909 information about the new prospective cohort at each assessment time point post donation
- 910 (Objectives b.1. and b.2.). Standard approaches to examine distributions of responses to survey
- 911 measures will be examined (e.g., descriptive statistics, box plots, histograms). To examine
- 912 prevalence of poor HRQOL outcomes in each identified domain, we will calculate the percentage of
- 913 the sample at each time point that report clinically significant difficulties within a given domain.
- 914 These rates, as well as mean scores on continuous measures, can be compared to norms for the
- 915 measures.
- 916 To examine temporal patterns over time, we will use both survival analysis and mixed effects
- 917 strategies. We will examine time to specific outcomes (e.g., onset of specific mental health
- problems) via survival analysis. We will examine temporal patterns of responses in each outcome
- 919 domain with mixed effects models. We will evaluate assumptions regarding missing data patterns

- 920 and mechanisms and engage in sensitivity analyses to test the stability of our models. To examine
- 921 risk factors for poor outcomes in the identified domains at (or by) a particular time point post-
- 922 donation, we will initially utilize regression-based strategies (linear, logistic, or Cox proportional
- hazard, depending on the outcome measure of interest) (Objective b.3.). We will also apply mixed
- 924 effects models to examine risk factors in relation to the trajectory of change in a given HRQOL
- 925 outcome over time.

926 4.4 Primary Aim 4: To study the effects of pressure and flow on the outcomes of LDLT

927 **4.4.1 Study Methods:**

Baseline assessment will include the standard clinical and demographics required for the Core

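### Section 4.3.9 claims more than .80 power for conventionally small differences with 319 donors; at the usual convention of d or h = 0.2 it is about 0.43, and the argument for keeping .80 after multiplicity correction does not hold

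*Protocol*

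**What the plan says.** Section 4.3.9 of the protocol sets the prospective cohort's size: "We anticipate a total sample size of 375 liver donors". It assumes that "attrition will range between 10% to 15" percent, which leaves 319 to 337 donors at the last wave.

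For the risk-factor objective it uses the lower figure: "With a sample of 319, utilizing a regression approach to examine donor outcome status at a" given time point, "with two-tailed alpha at .05, as many as 8" covariates, with those covariates themselves moderately associated with the outcome. On that basis it says "with the outcome, then our power to detect even conventionally small" differences is adequate. The metric is a difference in proportions or in means, and the stated level is above .80.

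The section then turns to mixed-effects models. Because these admit cases with incomplete data, it concludes that the effective "sample size will be the total cohort enrolled. Therefore, even if we apply corrections for multiple" comparisons, power for risk factor-outcome associations still exceeds .80. It gives no numeric effect size, covariate R-squared, exposure split, within-person correlation, correction method or corrected alpha.

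**The concern.** A conventionally small group difference normally needs a total sample in the high hundreds, so .80 at 319 looks too high by a wide margin. The protocol's own statement for the long-term cohort, just before section 4.3.4, points the same way. There 600 donors, even with half lost (300), are credited with more than .80 for moderate-sized effects. In section 4.3.9 only 19 more donors, at the same alpha, are credited with it for small ones.

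Identifying which donors are at risk is one of the three objectives in section 3.3.2, and section 3.3.2.1 states a hypothesis about ambivalence and perioperative complications. If the power statement stands, a non-significant risk factor could be taken as well-powered evidence of no association. At d = 0.2 a true effect would in fact be missed more often than found.

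**Working it through.** **Inputs from section 4.3.9.** Enrolled 375; attrition 10% to 15%; analysed 319; two-tailed alpha .05; up to 8 covariates; stated power above .80. Section 3.3.2 lists five domains of poor outcome.

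**Assumptions, because the protocol gives no figures.** Small means d = 0.2 (means) or h = 0.2 (proportions). Groups are 50:50, the best case, with 30:70 as a variant. Any correction is Bonferroni over five domains, alpha 0.05/5 = 0.01.

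**Sample size.** 375 × 0.85 = 318.75 and 375 × 0.90 = 337.5. The plan's 319 and 337 are reproduced.

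**Stated power.** For two groups with a share p in one of them, the noncentrality is d × sqrt(N × p × (1 − p)) and power is approximately Φ(noncentrality − z). With balanced groups at N = 319:

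- noncentrality = 0.2 × sqrt(319/4) = 0.2 × 8.930 = 1.786
- power = Φ(1.786 − 1.960) = Φ(−0.174) = 0.431; the noncentral t with 8 covariates gives 0.429
- h = 0.2 at base rates from 5% to 50% gives 0.42 to 0.43

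The stated figure of more than .80 is not reproduced. For comparison, N = 300 gives 0.2 × sqrt(75) = 1.732 and Φ(−0.228) = 0.41.

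**Variants at d = 0.2, one time point, alpha .05 (noncentral t).**

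| Variant | Power |
|---|---|
| N = 319, 30:70 split | 0.37 |
| N = 319, covariates explain 13% of variance (d becomes 0.2/sqrt(0.87) = 0.214) | 0.48 |
| N = 375, nobody lost | 0.49 |

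**What would be needed.** Total N for 80% power = 4 × (1.960 + 0.842)² / 0.2² ≈ 785, or 786 in two equal groups. At N = 319 the smallest d with 80% power is 2.80 × sqrt(4/319) = 0.314, or 0.315 by the t distribution; call it 0.32, rounding up. To reach .80 at d = 0.2 with 319 donors, the covariates would have to explain about 60% of outcome variance.

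**Other readings of small, N = 319, one time point.**

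- f-squared = 0.02, noncentrality 0.02 × 319 = 6.38: power 0.71
- an R-squared increment of 0.02 with covariate R-squared 0.13, so f-squared = 0.02/0.85: power 0.78
- the same increment with covariate R-squared of about 0.175: power reaches .80

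**After correction.** At alpha 0.01 and d = 0.2, one time point, power is 0.21 (N = 319) to 0.26 (N = 375).

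**Repeated measures.** Averaging m = 4 post-donation waves with common within-person correlation ρ multiplies the variance by (1 + (m − 1)ρ)/m. With ρ = 0.5 this is 2.5/4 = 0.625. For 375 donors with complete data and a constant effect, the effective d is 0.2/sqrt(0.625) = 0.253. Power is then 0.69 at alpha .05 and 0.45 at alpha 0.01. With ρ = 0.3 the figures are 0.80 and 0.59; with ρ = 0.7 they are 0.59 and 0.35.

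**The case against.** The strongest defence is that the protocol never defines small and expressly lets the covariates relate moderately to the outcome. Those covariates reduce residual variance, and on an R-squared-increment reading power is 0.78 to above .80 at 319. This stands as far as it goes. A reader might infer that 0.71, the f-squared figure, is the most the plan could deliver; it is not a ceiling. These readings do not rescue the sentence as written, though. It speaks of differences in proportions or means, and the covariate R-squared they need is not given.

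Second, the mixed model uses up to four post-donation assessments, so single-time-point figures understate it. A reader might infer that even 375 donors cannot reach .80. The documents do not support that: at d = 0.2 and an assumed correlation of 0.3, four-wave averaging reaches 0.80 uncorrected, and with f-squared = 0.02 and a correlation of 0.5 it gives 0.93 uncorrected and 0.81 corrected. But this gain comes from repeated observation, and the protocol does not state the correlation it depends on. The reason it gives is that incomplete cases are included.

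Third, the corrected-power statement restates no effect size and is conditional on a correction being applied. It therefore cannot be called numerically refuted, and a reader should not infer that alpha 0.01 over five domains is planned. It is an assumption made here to show scale.

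Finally, 375 comes from transplant volume and a two-year enrolment window, not from this calculation, so the sample size does not depend on the error.

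**Conclusion.** The single-time-point claim is wrong as written on its own metric. Assuming d or h = 0.2, 319 donors give about 0.43 with balanced groups, and 0.37 to 0.49 across the split, the 13% covariate adjustment and full retention of 375. The stated level is above .80.

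The mixed-model step is unsupported rather than disproved. Keeping incomplete cases avoids discarding data but does not supply the missing observations, so the effective sample is not automatically the total enrolled. At d = 0.2 with the assumed Bonferroni correction, power is 0.21 to 0.26 at one time point and about 0.45 for four averaged waves at correlation 0.5. Some readings do exceed .80, but only with inputs the protocol leaves out. The result rests on the assumed conventions for small, the assumed split and, for the corrected figures, the assumed alpha.

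**What to change.** In section 4.3.9:

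1. Replace the claim for small differences with a statement that 319 donors give 80% power, at one time point and two-tailed alpha .05, for d of about 0.32 in balanced groups.
2. Delete the statement that under a mixed model the effective sample size is the total enrolled.
3. Either drop the claim of more than .80 after multiplicity correction, or restate it with the effect size, covariate R-squared, within-person correlation and corrected alpha on which it relies.

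The cost is protocol wording and a less favourable power figure. Sample size, assessments and analyses do not change.
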